5. RESEARCH ABSTRACT

Please provide a brief description in LAY language (understandable to an 8th grade student) of the aims of this project.

Aging is the primary risk factor for Alzheimer's disease (AD) which is the most common form of dementia and among the fastest growing causes of morbidity and mortality in the United States. The risk factors for AD emerge during midlife and are similar to cardiovascular and cerebrovascular diseases. The impact of midlife vascular changes on the brain are worsened by poor lifestyle habits, including eating a diet that contains a lot of added sugars (e.g., ultra-processed foods containing high amounts of fructose). One effect of eating a high sugar diet is an elevation in blood triglycerides (TGs), which impairs blood vessel function by causing inflammation; however, it is not known whether eating a lot of added sugars affects the blood vessels in the brain. The purpose of this project is to determine if there is a link between added sugar intake and brain health in midlife adults. Our hypothesis is that eating excess added sugar impairs the structure and function of an area of the brain called the hippocampus by increasing plasma TGs and systemic inflammation. To test this, we will have people eat a high and low sugar diet for 10 days each (in a random order) and test how each diet affects their blood vessel function, the structure of their hippocampus, and their memory performance. We expect to show that eating a diet that contains a lot of added sugars worsens brain health compared to a diet that contains few added sugars. The data generated from this project will help us better understand risk factors for dementia and will be used to support a future grant proposal to the National Institutes of Health aimed at lowering added sugar intake in mid-life adults and individuals with mild cognitive impairment.

6. PROCEDURES Describe all procedures involving human subjects for this protocol. Include copies of all surveys and research measures.

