6.1 Study Design

We will conduct a single-blind, randomized-crossover, controlled feeding study (see *Protocol Schema on next page*). We will provide subjects with 10-days each of a research diet containing low sugar (LS; 5% of energy) vs. high sugar (HS; 25% of energy) in a random order, separated by a 2-week washout. Primary and secondary outcomes will be measured at baseline and at the end of each 10-day intervention.

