Cognitive Function – Memory function will be assessed by performance on the Hopkins Verbal Learning Test (HVLT-R), The Brief Visuospatial Memory Test (BVMT-R), and the NIH Toolbox Pattern Comparison and Flanker tests. The HVLT-T and BVMT-R have multiple versions to prevent learning tests. We will choose three versions of this test at the beginning of the trial and will administer a different version at each visit. The order will be counterbalanced to avoid any effect of test version on cognitive outcomes. The selected NIH Toolbox texts are less prone to learning effects.

Study Restrictions

Subjects must avoid over-the-counter medications for 48 hours, vigorous aerobic exercise or alcohol for 24 hours, and all food, supplements and caffeine for ≥ 12 hours before testing visit but will be allowed to consume water. There are no restrictions for Visit 1.1, unless this visit is combined with Visit 1.2, in which case the above restrictions apply.

Table 6.2. Table of Blood Tests

	Test #	Type	Volume	Visit 1.2	Visit 3.3	Visit 4.3
Screening Labs						
Comprehensive Metabolic Panel	322000	SST Serum	4 mL	X	X	X
Complete Blood Count	005009	EDTA Plasma	4 mL	X	X	X
Lipid Panel	303756	SST Serum	4 mL	X	X	X
Control Measures						
Hemoglobin A1C	001453	EDTA Plasma	4 mL	X	---	---
APOE genotype	504040	EDTA Plasma	4 mL	X	---	---
Blood Biomarkers						
Oxidative Stress/Inflammation	---	EDTA Plasma	4 mL	X	X	X

	---	SST Serum	4 mL	X	X	X				
PBMC's	---	EDTA Plasma	32 mL	X	X	X				
		Total Per Visit		60 mL (4TBL)	52 mL (3.5 TBL)	52 mL (3.5 TBL)				
				Total Volume for Study (mL)		164 mL (11 TBL)				
						Total Volume for Study (pints)				
						1/3 pint				

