7. STUDY POPULATION AND RECRUITMENT

Study Population – The target enrollment for this study is 200 healthy adult men and women between 50-64 years of age, with a target completion of 40 participants. This age group has been defined by NIH as being at high risk of accumulating cardiometabolic risk factors that preclude chronic age-related diseases¹⁵⁻¹⁷. To avoid any influence of baseline diet (e.g., chronic consumption of a high-sugar diet prior to enrollment), will only enroll those with a habitual intake of added sugar that is reflective of the average American intake (~13% of total calories) based on the National Health and Nutrition Examination Survey (NHANES)¹⁸. This will increase the likelihood of observing changes in our primary outcome variables in response to the proposed research diets which are designed to deviate from baseline proportion of added sugars by about 10% of calories in each direction. Importantly, even if

subjects are close to the upper or lower cutoff, we are still likely to observe changes in primary outcomes when placed on the opposite arm of the crossover. Because this is a pilot study, we will analyze the data after the first 5-10 participants have completed the trial and ensure that we are seeing an effect of the diets on the primary outcome variables. If we do not see an effect, we will amend the protocol to increase the duration and/or modify the composition of the diets.

To be eligible to participate, volunteers must meet the following specific enrollment criteria:

Inclusion Criteria:

- ability to provide informed consent;
- men and postmenopausal women aged 50-64 years;
- habitual intake of added sugars ≤15% of total calories¹⁸;
- systolic BP < 130 mmHg; diastolic BP < 90 mmHg¹⁹;
- body mass index (BMI) <30 kg/m² and % body fat < 25% for men and < 33% for women
- fasting triglycerides < 200 mg/dl (< 2.3 mmol/L)²⁰;
- LDL cholesterol <160 mg/dl (4.14 mmol/L)²¹
- fasting plasma glucose <126 mg/dl (<7.0 mmol/L) and hemoglobin A1C < 6.5% at screening²²;
- weight stable in the prior 6 months (≤ 2 kg weight change);
- blood chemistries indicative of normal liver enzymes and renal function (estimated glomerular filtration rate using the MDRD prediction equation must be >60 ml/min/1.73 m²)

Exclusion Criteria:

- current use of medications or supplements known to lower blood triglycerides or cholesterol (e.g., fibrates, statins, high dose niacin, high dose omega-3 supplement);

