Cover Page for Statistical Analysis Plan

Official Title: The effects of added sugar intake on brain blood flow and hippocampal function in midlife adults

ClinicalTrials.gov ID: NCT05211726

Protocol ID: 1760500

Date of Document: September 23, 2020

Statistical Analyses

The aims for this study will be tested using General Linear Modeling. For hypotheses H1a and H2a, a Profile Analysis (multivariate within-in subjects ANOVA) will be performed. If the omnibus test is significant, univariate within subject ANOVAs will be performed, testing the effect of diet (baseline, low sugar, and high sugar diets) on each outcome. The multivariate extension is being used to control for type-I error inflation that might occur because each aim has three primary outcomes (Aim 1: 24-hour SBP, arterial compliance, and cerebrovascular reactivity; Aim 2: HC stiffness, HC damping ratio, and delayed recall memory). All assumptions for these models will be tested, and data will be screened for outliers and influential cases. Assumptions of linearity, sphericity, and normality will be evaluated using Box-Cox, Mauchly's, and Shapiro-Wilk tests, respectively. Because some values are expressed as ratios, if the assumptions of the within subject's ANOVA cannot be satisfied by transformations suggested by the Box-Cox test then either the non-parametric Friedman test or a Generalized Linear Model will be used. Given the cross-over design, the order effect will be tested using the same model but the effect will just be time point (baseline, post diet 1, and post diet 2). If significant, the order effect will be included in the final model. A significant diet effect will be followed by pairwise comparisons using Fisher's LSD procedure. The alpha is set at 0.05 for each test. Exploratory analyses will be conducted for hypotheses H1b and H2b, using regression models testing the changes (from baseline) in each primary outcome from Aims 1a and 2a after the high sugar diet with the changes in TGs, markers of oxidative stress, and inflammation. Additionally, regression models will be used to explore whether changes in the primary outcomes from Aim 1 moderate the relation between the changes in the primary outcomes in Aim 2. This moderation will be tested by including the interaction effects of changes in outcomes from Aim 1 and 2 with the changes in TGs, markers of oxidative stress, and inflammation. During Year 2, the PI will work with the COBRE Core's lead biostatistician ([name]) to conduct an interim data analysis for an R01 proposal. The O'Brien-Fleming alpha boundary function will be used, the alpha for significance of the interim analysis is .0054 and for the final analysis is .0492.

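### The SAP's order test uses a three-level time point that includes baseline, so it mixes period with baseline-to-post change; added to the diet model as listed, it makes both baseline comparisons inestimable, while high versus low survives

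*SAP*

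**What the plan says.** All of the analysis rules are in the SAP, Statistical Analyses. After a significant multivariate profile test, univariate within-subject ANOVAs follow, "testing the effect of diet (baseline, low sugar, and high sugar diets) on each outcome". For order, the same model is refitted and "the effect will just be time point (baseline, post diet 1, and post diet 2" are its three levels. Then: "If significant, the order effect will be included in the final model". Finally, "A significant diet effect will be followed by pairwise comparisons using" Fisher's LSD, which for three diet levels means high–baseline, low–baseline and high–low. The SAP lists no two-level period term and no sequence term.

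The Protocol fixes the timing in Section 6.1: "Primary and secondary outcomes will be measured at baseline and at the end of each 10-day intervention". So there is one baseline, before the first diet, and none before the second. The Research Abstract (Section 5) states the question as whether a high-sugar diet "worsens brain health compared to a diet that contains few added sugars", that is, high versus low.

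**The concern.** Each factor has baseline as one level and splits the two post-diet visits differently. Baseline versus the average of the post-diet visits is therefore the same contrast in both. Two things follow.

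- The order test has 2 df, and only one of them (second post-diet visit versus first) concerns period. The other responds to any average movement away from baseline, including a genuine diet response.
- If the test is significant and the listed factor is added to the diet model, the two factors overlap and the comparisons with baseline lose their meaning. Software may still print values for them, but those values depend on which redundant column it drops.

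At stake are two of the three planned pairwise comparisons, and whether a reported order effect can be read as one.

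**Working it through.** **Inputs.** From the SAP: n = 30, three occasions, correlation .3, alpha .05 for each test, univariate effect d = .56, two sequences. Assumed: 15 subjects per sequence, no period effect, and the shift patterns shown below.

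**1. The SAP's own figure.** With f = d/2 = .28, λ = f² × n × 3/(1 − ρ) = .0784 × 30 × 3/.7 = 10.08. A noncentral F on 2 and 58 df gives power .797, against the stated .80. The figure reproduces.

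**2. Rank of the model** (30 subject columns plus the terms shown).

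| Model | Columns | Rank | High–baseline, low–baseline | High–low |
|---|---|---|---|---|
| Diet | 32 | 32 | estimable | estimable |
| Diet + 3-level time point | 34 | 33 | not estimable | estimable |
| Diet + 2-level period | 33 | 33 | estimable | estimable |

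The dependency is low + high = post 1 + post 2, since both sides equal "not baseline". It is structural: sample size, balance or random subject effects do not remove it. High–low has variance 2/30 = .0667 times the residual variance in all three models.

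**3. What the order test responds to when there is no period effect.** For a shift δ common to both diets, λ = n × (2/3)δ²/(1 − ρ).

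- δ = .3: 30 × .06/.7 = 2.57, rejection .27.
- δ = .5: 30 × .1667/.7 = 7.14, rejection .64.
- Only high sugar shifts .56: the average post-diet shift is .28 and λ = 30 × (2/3) × .0784/.7 = 2.24, giving about .24. Simulation gives .197, because the unmodelled diet difference inflates the residual.

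Simulated rejection rates (the bracket sets all correlations to .3; otherwise correlations across both outcome and occasion are .09):

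| Shift from baseline in SD (low, high) | One outcome | Three outcomes jointly |
|---|---|---|
| 0, 0 | .049 | not tabulated |
| −.28, +.28 | .035 | .041 [.039] |
| 0, +.56 | .197 | .210 [.329] |
| +.3, +.3 | .269 | .257 [.402] |
| +.5, +.5 | .644 | .668 [.885] |

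A test of second versus first post-diet visit alone, averaged over the sequences, rejects in 4.8% to 5.3% of trials in every no-period scenario tried.

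**4. Price of always fitting period.** For high–low, SE = √(2 × .7/30) = .216 and .56/.216 = 2.59. Power of the direct test is .7221 on 58 df and .7219 on 57 df.

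**5. A side effect of the pre-test.** Suppose both visits move .3 or .5 SD from baseline and the diets do not differ. The 2-df diet test then rejects in about .27 or .64 of trials, with or without a two-level period term. Under the SAP rule it rejects in only .07 or .08, because a flagged time point absorbs the baseline contrast and leaves high–low as the only diet test. The direct high–low test rejects in .05.

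**6. Power for high–low = .56 SD through the full chain** (multivariate gate, then the univariate steps). The last column replaces the SAP's gates by a joint Hotelling test of the three high–low differences, then 1 df per outcome.

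| Pattern (low, high) | SAP procedure | High–low Hotelling first |
|---|---|---|
| High only (0, +.56) | .58–.59 | about .65 |
| Symmetric (−.28, +.28) | .46–.48 | about .65 |
| Both upward (+.20, +.76) | .69 | about .65 |

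Ranges are from repeated simulation runs. With all correlations at .3 the pairs are .65 against .71, .56 against .71, and .70 against .70.

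**The case against.** The strongest reply is that the SAP sentence is loose. It uses time point to test order, and does not say in so many words that a second three-level factor enters the final model. The SAP's randomisation section speaks of diet order as Group A or Group B. Coded that way, as group by diet, the model has 34 columns and rank 34, and all three contrasts are estimable. That is correct, and if it or a period term was intended, the SAP need only say so. But neither is the factor listed in brackets, and the order test itself is mixed on any reading.

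Second, the harm to the main question is small. High–low is untouched by the aliasing. Section 7 of the Protocol describes diets "designed to deviate from baseline proportion of added sugars by about 10% of calories in each direction"; the symmetric pattern is nearest to that, and there the flag is raised in only about 4% of trials. This stands, and it limits how serious the point is.

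Third, the Protocol already guards against practice effects (Section 6.4, Cognitive Function): "The HVLT-T and BVMT-R have multiple versions to prevent learning tests", with a different version at each visit in counterbalanced order. The documents show no expected drift in the MRI or vascular outcomes. This stands too, but the flag needs no drift: a diet response with a non-zero average is enough.

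Fourth, no coding can separate a time change from an effect shared by both diets when there is only one baseline. That is a limit of the design, and the fix does not claim to remove it.

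**Conclusion.** The order test is wrong as written and should be changed before analysis. Its false-flag rate depends on the pattern of response: about 4%, 20% and 27% to 64% in the patterns above, given n = 30, correlation .3, balanced sequences and no period effect. When it flags and the listed factor is added, two of the three LSD comparisons are lost or arbitrary.

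Three stronger conclusions that a reader might infer are not supported.

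- *That the high-versus-low result is biased or lost.* It remains estimable with unchanged variance. Bias would need both a period effect and unequal completers by sequence, and the SAP plans balanced randomisation.
- *That the SAP rule declares a diet effect in 27% to 64% of trials under a common time change.* Those rates belong to the 2-df diet test without the pre-test; under the SAP rule they are .07 and .08.
- *That correcting the order term raises power.* For one outcome without the multivariate step, a direct high–low test has power .72 against .66 (high only) or .60 (symmetric) under the SAP rule. That gap comes from the 2-df diet gate, not from the order term. Through the full chain, the advantage of a direct test depends on the pattern and can reverse.

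**What to change.** 1. Delete the three-level order pre-test. Always include a two-level period term (post diet 1 = −1/2, post diet 2 = +1/2, baseline = 0), with sex as planned.
2. Base the diet conclusion on the period-adjusted high–low contrast. State that a significant 2-df diet test alone is not evidence of a diet effect. This must accompany item 1, because deleting the pre-test also removes its incidental protection of that test.
3. State that high–baseline and low–baseline can be read as diet effects only if there is no baseline-to-post time change, which one baseline cannot check. The exploratory H1b and H2b regressions are not touched by the rank problem, but they use changes from baseline and need the same caution.
4. Optional: replace the multivariate and omnibus gates by a joint high–low test. This changes the primary analysis and is a trade-off, so it should be argued on the question asked and not on a general gain in power.

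Items 1 to 3 cost SAP wording and one error degree of freedom (58 to 57 at n = 30). Visits, data and sample size do not change.

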10. DATA

Will subjects be anonymous to the researcher? No.

If subjects are identifiable, will their identities be kept confidential? (If yes, please specify how)

Subjects will not be individually identified, except by a subject ID number known only to the investigators.

How will data be stored and kept secure (specify data storage plans for both paper and electronic files. For guidance see <http://www.udel.edu/research/preparing/datasstorage.html>)

Physical data will be stored in a locked file cabinet in the PI's lab space and will only be accessible by

members of the research team. Physical data that are transcribed into an electronic database, and electronically captured data will be kept on a password protected laboratory server that is maintained by the University of Delaware. Electronic data will be periodically backed-up onto an external hard drive that will be kept in a locked office space. All of the ultrasound images and files generated by the SpphygmoCor and RespirAct devices will be coded with an identification number and will not contain the name of the subject. The names of subjects will not be identified in any publication arising from these studies. Only the PI and research staff will have access to data from this study.

How long will data be stored? All data will be stored in a locked cabinet or a password protected computer indefinitely.

Will data be destroyed? YES NO (if yes, please specify how the data will be destroyed)

Will the data be shared with anyone outside of the research team? YES NO (if yes, please list the person(s), organization(s) and/or institution(s) and specify plans for secure data transfer)

The data may be shared with the National Institutes of Health. The trial will be registered with clinicaltrials.gov once the funding is finalized; however, only de-identified data will be reported.

How will data be analyzed and reported?

Data will be aggregated and reported as group means or as de-identified, individual data points. Because this study is intended to support a larger R01 proposal, we will analyze the data after the first 5-10 subjects have completed all testing. If we do not observe any effect of the diet on primary outcomes, we will consider amending the protocol to increase the duration of the controlled feeding window and/or modify the composition of the diets. Any subjects tested prior to a major amendment of the protocol will be replaced to achieve the target sample size.

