
Randomization, Blinding, Power & Sample Size

To enhance scientific **rigor and reproducibility**, subjects will be randomized to diet order with Group A receiving the high sugar diet first followed by the low sugar diet and Group B receiving each diet in the opposite order. Investigators responsible for data collection or analysis will be blinded to treatment condition. To address **sex as a biological variable**, we will use a block randomization scheme to ensure an even number from each sex within each treatment group and will covary for sex in our analyses. A major objective is to generate preliminary data and conduct a power analysis for an eventual R01. Power for this pilot study was determined for the profile analysis for Aims 1 and 2, testing the change across the three measurement occasions for three outcomes. This study is adequately powered (power = .80), with n=30 to detect a moderate effect ($d=.46$), for three outcomes and three timepoints with nominal alpha (.05), assuming a conservative correlation among the outcomes and repeated measures of 0.3. If the multivariate test is significant, this study is adequately powered (power = .80), with n=30 to detect a moderate effect ($d=.56$), for three timepoints with nominal alpha (.05), assuming a correlation among the repeated measures of 0.3 for follow-up univariate within subject ANOVAs. To account for drop-out or experimental error, our total recruited sample size will be 40. This effect size matches ones seen in the literature, which found a moderately large effect ($d = 0.69$ with $n=14$) in the effect of increased serum TGs within 4-5 days of a high fructose meal⁷⁵.

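### The SAP's O'Brien-Fleming levels of .0054 and .0492 do not form a 5% pair at the half-way look they imply (overall error 0.0513), and the SAP also sets 0.05 for each test

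*SAP*

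**What the plan says.** The SAP's Statistical Analyses section sets a general level: "The alpha is set at 0.05 for each test". It ends with an interim analysis in the study's second year, whose purpose is "to conduct an interim data analysis for an R01 proposal". For that look, "The O'Brien-Fleming alpha boundary function will be used", and "the alpha for significance of the interim analysis is .0054 and for the final analysis is .0492". The section gives no number of completers or information fraction at the interim and no sidedness. It does not say which tests (omnibus, univariate or pairwise) the two levels govern.

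The SAP's power section uses n = 30, "for three outcomes and three timepoints with nominal alpha (.05"), and plans to recruit 40. Protocol section 7 describes enrolment "with a target completion of 40 participants".

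The protocol also describes an early look. Section 7 says "we will analyze the data after the first 5-10 participants have completed the trial", and section 10 says "we will analyze the data after the first 5-10 subjects have completed all testing". Section 10 ties this look to the same grant proposal. In both sections the purpose is to see whether the diets have an effect and, if not, to amend their duration or composition. Neither document says whether this is the SAP's interim.

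**The concern.** A group-sequential pair of levels exists to keep the overall error at its stated value across the looks. For O'Brien-Fleming, the interim level, the final level and the timing of the look are tied together: fixing the overall error and the timing fixes both levels. The interim level of .0054 is close to standard values for a look at 50%, but .0492 is not the final level that goes with it.

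Two things are at stake. Used at the timing it implies, the pair does not deliver the 5% it is meant to protect. And because 0.05 for each test stands in the same section, the final threshold is open to choice after the results are known.

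**Working it through.** **Inputs.** Interim level .0054, final level .0492, O'Brien-Fleming boundary, one interim (SAP, Statistical Analyses). n = 30 for power and 40 recruited (SAP, power section). A look at 5-10 completers (protocol sections 7 and 10). Assumptions: two-sided tests and a normal approximation, although the planned tests are F tests.

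**Step 1: the timing the pair implies.**
- z(.0054/2) = 2.7822 and z(.0492/2) = 1.9669.
- O'Brien-Fleming sets z_interim = z_final/√t, so t = (1.9669/2.7822)² = 0.4998.
- The pair therefore has the shape of one look at 50% information, which is 15 of 30 or 20 of 40.

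**Step 2: overall error at that timing.** With correlation √t between the two statistics, overall error = 1 − P(|Z1| < 2.7822 and |Z2| < 1.9669).
- At t = 0.5 numerical integration gives 0.05129, and simulation agrees (0.0513).
- Rounding of the stated levels does not explain the excess. The range .00535-.00545 with .04915-.04925 gives 0.0512 to 0.0514.

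**Step 3: what would match at 50%.** Solving for an overall 0.05:
- interim .0054 kept: final .0479;
- final .0492 kept: interim .0026.

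| Method at t = 0.5 | Interim | Final |
|---|---|---|
| Exact O'Brien-Fleming (c = 1.9774) | .0052 | .0480 |
| Spending 2(1 − Φ(1.960/√t)) | .0056 | .0478 |
| Spending 4(1 − Φ(2.2414/√t)), i.e. twice one-sided 0.025 | .0031 | .0490 |

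Each of these pairs returns 0.0500 in the same calculation. No variant tried reproduces .0054/.0492 at 0.05.

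**Step 4: other timings for the stated pair.** Overall error is 0.0500 at t = 0.70 and 0.0497 at t = 0.75. The pair holds 5% only from about 70% information onward, where under the normal approximation it no longer has the O'Brien-Fleming shape.

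**Step 5: the 0.05 statement.** An interim test at .0054 and a final test at .05 give 0.0521 at t = 0.5.

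**Step 6: only if the interim is the protocol's early look.** The fraction is then between 5/40 = 12.5% and 10/30 = 33%.

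| Completers at the look | Overall error with .0054/.0492 |
|---|---|
| 10 of 30 | 0.0524 |
| 10 of 40 | 0.0529 |
| 5 of 30 | 0.0534 |
| 5 of 40 | 0.0536 |

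Exact O'Brien-Fleming would then need an interim p below about 0.0007 at 10/30, or 0.00009 at 10/40.

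**Step 7: power cost.** Take a within-subject F(2, 58) test, n = 30, with noncentrality set for 80% power at .05. Power is 79.8% at .0492 and 79.5% at .0480.

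**The case against.** The strongest reply is that the SAP states neither the 50% timing nor the sidedness, so 0.0513 rests on inference. That is true. But a match of 0.4998 is hard to put down to chance, the one-sided reading still gives 0.0509 at 50%, and the timings that rescue the pair do not fit the boundary the SAP names.

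The match to 50% also belongs to a one-degree-of-freedom test, whereas the plan uses multivariate and three-level tests. If the shape is applied to a chi-square statistic, the pair implies about 58% information at 2 df and 69% at 6 df, with simulated overall error of about 0.0508-0.0509 and 0.0504-0.0505. So the implied timing is less certain than 0.4998 suggests, and the excess is smaller at those timings. It does not disappear. If the look is at 50%, the excess is slightly larger than the normal figure: 0.0517 for a 6-df test and 0.0518-0.0519 for paired t-tests at n = 30-40.

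An interim that serves only a grant proposal may make no claim. A final test at .0492 alone then has an error of .0492, below 5%. This stands, but the SAP sets a level for significance at the interim, which reads as a test, so the point needs settling.

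The 0.05 per test can be read as the overall level before it is split between looks, with the later, specific sentence governing. That reading is reasonable, but the text does not give it, and the power calculation also uses .05. The window affected is only .0008 wide.

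Finally, the 5-10 completer figures are conditional. Protocol section 10 replaces subjects tested before a major amendment, so after such an amendment the two-look formula may not apply. Those figures carry no weight in the conclusion.

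**Conclusion.** The concern holds, as a minor one. The two stated levels do not belong together: at the half-way look their shape implies, overall two-sided error is 0.0513, an excess of 0.13 percentage points. The result assumes two-sided tests, the normal approximation, and an interim at which significance can be claimed. The competing 0.05 is a secondary ambiguity in the same threshold. The missing interim timing is the reason the levels cannot be confirmed from the documents. The effect on the trial's conclusions is small, but a threshold set to protect 5% should do so as written.

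**What to change.** State the number of completers at the second-year interim, the sidedness, and whether this is the protocol's 5-10 completer look. Then take one of two routes.

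- **If an efficacy claim can be made at the interim:** derive both levels for that fraction, name the method, list the tests they govern, and say that they replace 0.05 for the primary tests. At 50% the choices are .0052/.0480, .0056/.0478 or .0031/.0490, or .0054 kept with a final level of .0479.
- **If the look only supplies planning estimates for the grant proposal:** say that no significance test is done at the interim, delete both levels, and test the final analysis at 0.05.

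Either way the change is a few words in the SAP. Moving the final level from .0492 to .0480 costs about 0.3 points of power (79.8% to 79.5%), or 0.5 points against testing at 0.05. The second route costs no power.

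### The .80 quoted for the follow-up univariate ANOVAs is the power of an ungated ANOVA; the chance of passing both the multivariate test and the ANOVA is not reported and is lower in most scenarios

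*SAP*

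**What the plan says.** Under Statistical Analyses, the SAP groups the primary outcomes in threes: "each aim has three primary outcomes (Aim 1: 24-hour SBP, arterial compliance, and cerebrovascular reactivity; Aim 2: HC stiffness, HC damping ratio, and delayed recall" (a memory measure). Each aim is tested first by a profile analysis of its three outcomes. The single-outcome tests come second and are conditional: "If the omnibus test is significant, univariate within subject ANOVAs will be performed, testing the effect of diet (baseline, low sugar, and high sugar diets"). The rule for significance levels is "The alpha is set at 0.05 for each test", and for the interim look it adds that "the alpha for significance of the interim analysis is .0054 and for the final analysis is .0492".

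Under Randomization, Blinding, Power & Sample Size, the SAP gives two power statements. For the multivariate test: "This study is adequately powered (power = .80), with n=30 to detect a moderate effect ($d=.46$), for three outcomes and three timepoints"; the correlation is described there as "assuming a conservative correlation among the outcomes and repeated measures of 0.3". For the second step: "If the multivariate test is significant, this study is adequately powered (power = .80), with n=30 to detect a moderate effect ($d=.56$), for three timepoints".

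The SAP gives no probability of passing both steps. It does not name the multivariate statistic. It does not say how many of an aim's three outcomes are assumed to respond, or in which direction they move relative to the 0.3 correlation.

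**The concern.** A diet effect on 24-hour SBP, hippocampal stiffness or any other primary outcome can be declared only if two tests are significant in the same data. A power figure for the second test alone does not describe that procedure. A reader who sees n=30 called adequate at .80 will expect a d=.56 effect on a primary outcome to be missed about one time in five.

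If the true two-step figure is lower, a null result on an outcome is weaker evidence than it appears. The study also names a power analysis for a later R01 as a major objective, so the same omission could carry over into that application.

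**Working it through.** **Inputs from the SAP.** n=30, d=.56, three occasions, three outcomes per aim, alpha .05 at each step, correlation 0.3 among occasions and among outcomes.

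**Step 1: reproduce the stated .80.** Read d as 2f, the reading that recovers the SAP's number, so f = .56/2 = .28. For a one-group repeated-measures ANOVA under sphericity:

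- lambda = n × k × f² / (1 − rho) = 30 × 3 × .0784 / .7 = 10.08
- df = 2 and 2 × 29 = 58
- power at alpha .05 = .797; at the final alpha .0492 it is .795
- d for exactly .80 = .562

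The stated figure is reproduced with no multivariate test in the calculation.

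**Step 2: bound the two-step probability.** Passing both tests cannot be more likely than passing the ANOVA alone. The chance of declaring an effect on a given outcome is therefore at most .797 at n=30.

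**Step 3: simulate the two steps.** Multivariate normal data, three outcomes by three occasions, both correlations .3, a linear mean pattern with f=.28 on each responding outcome, sex not modelled, 20,000 or more runs per case (simulation standard error below .004). Two gates were tried, because the SAP does not name one:

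- Hotelling T2 on the six diet contrasts (df 6 and 24).
- The sphericity-based Wilks test (three outcomes, 2 hypothesis df, 58 error df).

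An effect on the named outcome counts only if both the gate and its ANOVA have p < .05.

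| Outcomes responding at d=.56 (n=30) | Both steps, T2 | Both steps, Wilks | ANOVA given gate, T2 | ANOVA given gate, Wilks |
|---|---|---|---|---|
| Named outcome only | .56 | .64 | .94 | .94 |
| Two, same direction | .70 | .75 | .87 | .86 |
| Three, same direction | .72 | .76 | .86 | .85 |
| Two, opposed | .78 | .79 | .81 | .80-.81 |
| Three, one opposed | .79 | .79 | .80 | .79-.80 |

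Same direction means that the outcomes move together with the positive correlation; opposed means that one moves against it.

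**Step 4: other assumptions.** If the other two outcomes respond at a quarter to a half of d=.56, the two-step figure is .51-.54 (T2) or .58-.62 (Wilks). Varying the correlation among outcomes from 0 to .5 under T2 gives .50 to .80. The overall range is about .50-.80.

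**Step 5: 40 completers.** The ungated ANOVA has lambda = 40 × 3 × .0784 / .7 = 13.44, df 2 and 78, and power .906. The two-step figures in the same-direction cases are .76, .87-.88 and .88 (T2, for one, two and three responding) and .80-.81, .89 and .90 (Wilks). Opposed directions give about .91.

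**Step 6: d at which both steps together reach .80 (n=30, same direction).** T2: roughly .60-.62 if two or three respond, about .70 if one responds. Wilks: about .59 and .65.

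**The case against.** The strongest reply is that the SAP never claims an overall probability. It gives one power for each test and introduces the second with a condition on the first. Reporting power test by test is common in gated plans. Taken as a strictly conditional figure, .80 is conservative in the same-direction cases, where the power given a passed gate is .85-.94. This stands to the extent that there is no arithmetic slip. It does not make .80 the right figure for outcome-level conclusions. The number is computed without the gate, and it matches the conditional power only where the gate almost always passes, a scenario that the SAP does not state.

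A reader might also infer that 56-72% is the plan's own two-step power. The documents do not support that. The range needs a Hotelling T2 gate and effects aligned with a positive correlation, and the SAP specifies neither. Worse vascular health could mean SBP up with compliance and reactivity down. Taken with a literal +0.3 correlation, that pattern gives about .79 and almost no shortfall. Further, if the SAP's gate power of .80 at d=.46 is accepted as given and all three outcomes respond at d=.56, the gate power is about .94. The two-step probability is then at least .797 + .94 − 1, or about .74.

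Finally, this is a pilot. Protocol section 7 targets 40 completers and replaces withdrawals. At that number only the sole-responder case under T2 falls clearly below .80. This limits the consequence, but the SAP's own claim is made at n=30.

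**Conclusion.** The point holds as one of labelling and omission. The .80 at d=.56 and n=30 is ungated ANOVA power, the plan gates that ANOVA, and the probability of passing both steps is unreported. That probability cannot exceed about .80.

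In every case computed with same-direction effects and correlations of .3, it falls short: .56-.72 under T2 and .64-.76 under Wilks. If only one of an aim's outcomes responds, the miss rate is 1 − .64 = 36% to 1 − .56 = 44%, not 20%. Across the choices left open, about .50-.80 is the defensible range, and no single value inside it can be called the plan's power.

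These figures rest on d being read as 2f, normal data, sphericity and the assumed response patterns. The documents do not show that the stated .80 was miscalculated or that more participants are needed.

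**What to change.** In the SAP's Randomization, Blinding, Power & Sample Size section:

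- Label .80 at d=.56 as the power of the univariate ANOVA without the multivariate gate, and do not use it alone to call n=30 adequate for outcome-level conclusions.
- Name the multivariate statistic, the number of outcomes per aim assumed to respond, and the sign of the correlations relative to the effects.
- Report the probability of passing both steps under those assumptions, with a range over the plausible alternatives, and the d at which it reaches .80.
- Give the same figures for the 40 completers targeted in protocol section 7.

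Any number taken from the table above must carry its gate and its effect directions, since it is wrong under other readings of the plan. No test, decision rule or enrolment figure changes. The cost is a short simulation, a few sentences and a somewhat less favourable stated power.
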